## 11.7. Brief Psychiatric Rating Scale for Children (BPRS-c)

The Brief Psychiatric Rating Scale for Children (BPRS-c) is a clinician-rated tool designed to assess the severity of psychopathology in subjects with schizophrenia and other psychotic disorders. The BPRS-c is a 21-item, clinician-based rating scale designed for use in evaluating psychiatric problems of children and adolescents. The severity of each item of the BPRS-c is rated on a scale of 0 (not present) to 6 (extremely severe) (total score range: 0 to 126). Higher scores represent greater symptom severity. The BPRS-c will be administered only to subjects  $\geq$ 3 years of age. Items that are not scored are left blank (ie, not scored as "0"). Rather than using the EDC total score value, the total score for BPRS-c will be re-calculated as the sum of ratings for each of the 21 items. Missing items will be imputed based on the average score of the other items at that assessment; however, if >50% of the items are missing for that subject/visit, then the total score will be set to missing.

BPRS-c total score observed and change from baseline values will be summarized with descriptive statistics by visit and treatment group. This summary will be produced for the DB period and the OL period separately. The study baseline will be used for the DB period summaries while the OL baseline will be used for the OL period summaries.

### **11.8.** Prior and Concomitant Medications

Prior medications and concomitant medications, including glucocorticoids and mineralocorticoids, will be summarized by World Health Organization (WHO) Drug Anatomical Therapeutic Chemical Classification (ATC) Level 3 category (or Level 2 if there is not an applicable Level 3 category) and preferred name. Concomitant medications will be summarized separately for the DB and OL periods.

Medications will be assigned to study periods (prior, concomitant in the DB period, and/or concomitant in the OL period) based on the medication start and stop dates relative to study drug dosing in the DB and OL periods. Medications that were started and stopped prior to the date of the first dose of study drug in the DB period will be assigned as prior. Medications that had a stop date or were ongoing during the DB period will be assigned as concomitant in the DB period. Medications that had a stop date or were ongoing during the OL period will be assigned as concomitant in the DB period.

Within each summary, the number and percentage of subjects using medications in each WHO Drug ATC category (Level 3/preferred name) will be summarized by treatment group. A subject may take the same medication more than once or multiple medications for a subject may be classified under the same ATC level or preferred name. A subject is counted only once for each level of medication classification within a summary. The tables will be sorted alphabetically by ATC code.

# **12.** PATIENT AND CAREGIVER REPORTED OUTCOMES

Patient and caregiver reported outcomes capture the status of a subject's health condition and come directly from the subject or caregiver, without interpretation of the subject's or caregiver's response by a clinician or anyone else. The following section describes the assessments that were administered to subjects and caregivers throughout the study and the methods of scoring and summarizing these data. All outputs for the summaries will be based on the Full Analysis Set for the DB period and on the OL Period Safety Analysis set for the OL period. The analysis of the data will be based on descriptive statistics and presented by treatment group according to the study visit unless otherwise noted. These data will not be imputed. No formal hypothesis-testing analysis of patient and caregiver reported outcomes data will be performed. Unless otherwise noted, the below summaries will be produced for the DB period and the OL period separately and will follow the treatment-period specific treatment group and baseline definitions (as described in Section 6) where the study baseline will be used for the DB period summaries and the OL baseline will be used for the OL period summaries.

# 12.1. EuroQoL 5 Dimensions (EQ-5D) and Visual Analog Scale (EQ-VAS)

The EQ-5D-Y was administered to subjects 8 to 15 years of age. This instrument has subjects self-report on 5 dimensions of health: Mobility, Looking After Myself, Usual Activities, Pain/Discomfort, and being Worried, Sad, or Unhappy. Each dimension has 3 levels of severity: no problems, some problems, or a lot of problems. The subject indicates his/her health state by checking the box next to the most appropriate statement. The number and percentage of subjects in each of the 3 levels for each dimension at baseline and each postbaseline visit will be summarized by treatment group.

The EQ-5D-5L was administered to subjects  $\geq 16$  years of age. The EQ-5D-5L is a general, single index measure for describing and valuing health. It defines health in terms of 5 dimensions: Mobility, Self-Care, Usual Activities, Pain/Discomfort, and Anxiety/Depression. Each dimension has 5 levels: no problems, slight problems, moderate problems, severe problems, and extreme problems. The subject indicates his/her health state by checking the box next to the most appropriate statement. Number and percentage of subjects in each of the 5 levels for each dimension at baseline and each postbaseline visit will be summarized by treatment group.

For both the EQ-5D-Y and the EQ-5D-5L, subjects rated their overall health on a 0 to 100 hashmarked, vertical visual analogue scale (EQ-VAS). The endpoints are labeled 'The best health you can imagine' (100) and 'The worst health you can imagine' (0). The EQ-VAS score observed and change from baseline values will be summarized at baseline and each postbaseline visit by treatment group and age subset (ie, 8 to 15 years of age vs.  $\geq$  16 years of age).

The above summaries will be produced for the DB period and the OL period.

# 12.2. Pediatric Quality of Life Instrument (PedsQL)

The 23-item Pediatric Quality of Life Instrument (PedsQLTM) Generic Core Scales encompass: 1) Physical Functioning (8 items), 2) Emotional Functioning (5 items), 3) Social Functioning (5 items), and 4) School Functioning (5 items) (Varni et al., 2001). The instructions ask how much of a problem each item has been during the past one month. A 5-point Likert response scale is used (0=never a problem; 1=almost never a problem; 2=sometimes a problem; 3=often a

problem; 4=almost always a problem). For ages 5 to 7, the response scale is reworded and simplified to a 3-point scale (0=not at all a problem; 2=sometimes a problem; 4=a lot of a problem), with each response choice anchored to a happy-to-sad faces scale. Items are reverse-scored and linearly transformed to a 0 to 100 scale, so that higher scores indicate better health-related quality of life. The mean score will be calculated as the sum of the items divided by the number of items answered. If more than 50% of the items in the scale are missing, the scale scores will not be computed. If 50% or more items are completed, the mean of the completed items in the scale will be calculated. The psychosocial health summary score will be calculated as the sum of the items divided by the number of items answered in the emotional, social, and school functioning scales. The physical health summary score will be calculated as the physical functioning scale score. The total score will be calculated as the sum of all the items divided by the number of items answered on all the scales.

The psychosocial health summary score, the physical health summary score, and the total score observed and change from baseline values will be summarized with descriptive statistics by visit and treatment group. This summary will be produced for the DB period and the OL period. Subject and parent reports will be summarized separately.

### 12.3. Pediatric Quality of Life Family Impact Module

The PedsQL Family Impact Module is a 36-item instrument that include 6 scales measuring parent/caregiver self-reported functioning: 1) Physical Functioning (6 items), 2) Emotional Functioning (5 items), 3) Social Functioning (4 items), 4) Cognitive Functioning (5 items), 5) communication (3 items), 6), Worry (5 items), and 2 scales measuring parent-reported family functioning; 7) daily Activities (3 items) and 8) Family Relationships (5 items) (Varni et al., 2004). A 5-point response scale is used (0=never a problem; 4=always a problem). Items are reverse-scored and linearly transformed so that higher scores indicate better functioning. The mean score will be calculated as the sum of the items divided by the number of items answered. If more than 50% of the items in the scale are missing, the scale scores will not be computed. If 50% or more items are completed, the mean of the completed items in the scale will be calculated. The parent HRQL summary score (20 items) will be computed as the sum of the items divided by the number of items answered in the physical, emotional, social, and cognitive function scales. The family functioning summary score (8 items) will be computed as the sum of the items divided by the number of items answered in the daily activities and family relationships scales. The total score will be calculated as the sum of all 36 items divided by the number of items answered.

The parent HRQL summary score, the family functioning summary score, and the total score observed and change from baseline values will be summarized with descriptive statistics by visit and treatment group. This summary will be produced for the DB period and the OL period.

# 13. OTHER DATA

### 13.1. Ease of Administration and Palatability of Study Drug – DB Period

The acceptability/ease of administration and palatability of the study drug at Week 4 is a secondary endpoint and was assessed via questionnaire. Palatability of the study drug was assessed by asking subjects  $\geq 6$  years of age to rate the taste and smell of the study drug, as well as how easy the study drug was to take, on a 5-point hedonic scale, with 5 being a favorable response and 1 being an unfavorable response. Each response was anchored to a face on a happy-to-sad scale. For subjects 2 to 5 years of age, caregivers were asked to rate the ease of administration of the study drug both on that day and overall on a 5-point hedonic scale with 5 indicating relative ease and 1 indicating relative difficultly.

The three questions related to ease of administration, taste, and smell will be summarized on the Full Analysis Set with descriptive statistics by treatment group, formulation type (oral solution vs. capsule), and age group (> 2 to < 6 years;  $\ge$  6 years) at Week 4.

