## 8.1. Subject Inclusion Criteria

To participate in this study, subjects must meet the following criteria:

- 1. Have documentation of witnessed written or oral pediatric assent from the subject deemed capable of providing assent, and written informed consent from the subject's parent(s) or legal guardian(s) (or the subject, if the subject has reached the age of majority) in accordance with the governing IRB/IEC and according to local laws and regulations.
- 2. Be a female or male 2 to 17 years of age with a body weight of at least 10 kg.
- 3. Have a medically confirmed diagnosis of classic CAH due to 21-hydroxylase deficiency based on standard medically accepted criteria such as elevated 17-OHP level, confirmed CYP21A2 genotype, diagnostic results after cosyntropin stimulation testing.
- 4. Be on a supraphysiologic glucocorticoid dose regimen defined as >12 mg/m²/day in hydrocortisone dose equivalents (see Section 9.3.2) that has been stable for at least 1 month prior to screening, is intended for chronic use, and consists ONLY of 1 or more of the following orally administered glucocorticoids: hydrocortisone, prednisone, prednisolone, or methylprednisolone. Subjects must be receiving a morning dose of glucocorticoid.
- 5. Have an A4 level (prior to the morning glucocorticoid dose) greater than the midpoint of the reference range, according to sex and either age (for Tanner stage 1) or pubertal stage (for Tanner stages 2 to 5).
- 6. Have a 17-OHP level (prior to the morning glucocorticoid dose) >2 × ULN according to sex and either age (for Tanner stage 1) or pubertal stage (for Tanner stages 2 to 5).
- 7. If treated with fludrocortisone, dose should be stable for at least 1 month prior to screening. Regardless of fludrocortisone treatment, upright plasma renin activity (PRA) (in the absence of medications that confound interpretation of PRA) during screening should be <3 × ULN and >lower limit of normal on the subject's usual sodium intake (if PRA >2 × ULN and <3 × ULN, subject must have normal age-specific systolic blood pressure and heart rate and serum potassium <ULN [Harman et al., 2011]).

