## 9. STUDY EVALUATIONS

#### 9.1. Schedule of Assessments

A schedule of assessments for the screening period; the double-blind, placebo-controlled treatment period; and the open-label treatment period is shown in Table 7, and a schedule of assessments for the OLE is shown in Table 8.

Prior to any study-related procedures, parental or legal guardian (or subject, if the subject has reached the age of majority) informed consent with signed and witnessed study subject assent will be obtained (which may be done remotely, if allowed and remote consenting procedures are in place), as required by the governing IRB or ethics committee and according to local laws and regulations. At Week 52, the subject's parent(s) or legal guardian(s) (or the subject, if the subject has reached the age of majority) will review applicable portions of the ICF and the subject will review applicable portions of the assent form (if applicable) and confirm whether the subject will participate in the optional OLE for continued access to crinecerfont (Table 8). Subject-related events and activities including specific instructions, procedures, concomitant medications, dispensing of study drug, and descriptions of AEs should be recorded in the appropriate source documents and eCRFs.

All assessments during the core study as well as the OLE that are performed based on the subject's age should be based on the age at time of initial informed consent, unless otherwise specified.

Table 7: Schedule of Assessments – Double-Blind Placebo-Controlled and Open-Label Treatment Periods

Assessment	Screening Period a,b Double-Blind, Placebo-Controlle			led Treatr	ed Treatment Period a		Open-Label Treatment Period a			Follow-up Period for Subjects Not Entering the OLE a				
	Week -4 to Day -1	Day 1 (Baseline)	Week 4	Week 8	Week 12	Week 16	Week 20	Week 28	Week 32 b,d	Week 36 b,c	Week 4	Week 44b,	Week 52/ ET	Week 56°
Informed consent/assent	X	,												
Inclusion/exclusion criteria	X	Update												
Medical history	X	Update												
TSH and free T4	X (TSH only)	X						X					X	
UDS f	X													
Physical exam	X	X						X					X	
Tanner stage g	X	X				X		X			X		X	
Vital signs, height, weight h	X	X	X			X		X			X		X	X
Hematology/coagulation	X	X				X		X			X		X	X
Chemistry, cortisol	X	X		X	X	X		X	X	X	X		X	X
Urinalysis	X	X						X					X	X
CYP21A2 genotyping			X											

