## 9.6. Other Assessments

## 9.6.1. Palatability/Ease of Administration Assessment

Palatability of the study drug will be assessed by asking subjects  $\geq 6$  years of age to rate the taste and smell of the study drug, as well as how easy the study drug was to take, on a 5-point hedonic scale, with 5 being a favorable response and 1 being an unfavorable response. Each response is anchored to a face on a happy-to-sad scale. Subjects who found the taste to be "1 - Very Bad" or "2 – Bad" will be asked to identify what quality(ies) about the taste they didn't like. Palatability assessment at the early termination visit is not required if the subject has discontinued study drug.

For subjects 2 to 5 years of age, caregivers will be asked to rate the ease of administration of the study drug both on that day and overall on a 5-point hedonic scale with 5 indicating relative ease and 1 indicating relative difficulty. This assessment is adapted from the Caregiver-administered Children's Acceptance Tool, which has been shown to be a reliable instrument in assessing pediatric acceptance of medicines (Blume et al., 2018).

The palatability/ease of administration assessment should be administered within approximately 15 minutes after study drug dosing as specified in Table 7.

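### The palatability and ease-of-administration tables use a lower age group that starts above 2 years, so 2-year-olds fall in neither group if age is held in whole years

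*SAP*

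**What the plan says.** SAP 13.1 gives the ratings formal standing, stating that "palatability of the study drug at Week 4 is a secondary endpoint". The questions on ease, taste and smell "will be summarized on the Full Analysis Set with descriptive statistics by treatment group", by formulation and by age group. The lower group is printed as "age group (> 2 to < 6 years" and the upper group is ≥ 6 years. SAP 13.2 uses the same two groups for Week 28 (as the open-label baseline) and Week 52.

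Two-year-olds are in the trial and are assessed:

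- Protocol 8.1, inclusion criterion 2: "Be a female or male 2 to 17 years of age with a body weight of at least 10 kg".
- Protocol 9.6.1: "For subjects 2 to 5 years of age, caregivers will be asked to rate the ease of administration".
- SAP 13.1, in the paragraph just before the age groups: "For subjects 2 to 5 years of age, caregivers were asked to rate the ease of administration".

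On which age counts, Protocol 9.1 says that assessments performed by age "should be based on the age at time of initial informed consent, unless otherwise specified". The SAP does not say whether age is held in whole years or as a decimal when the groups in 13.1 and 13.2 are formed.

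**The concern.** The lower bound is open. A child whose recorded age is 2 satisfies neither condition, although the same section says that this child's caregiver is asked for a rating. SAP 13.1 describes no all-ages summary that would bring such a child back. By contrast, the blood pressure summary in SAP 11.4 is given by age category and for all ages combined.

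What is at stake is the completeness of a secondary-endpoint table. The caregiver-rated group spans only four whole-year ages and is then divided by treatment (2:1) and by formulation, so its cells are likely to be small. A reader would expect the lower group to contain everyone whose caregiver was asked, and nothing in the table would show otherwise.

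**Working it through.** The plan states no figure to reproduce here. The check is to assign each eligible age to the groups as written.

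**Inputs.** Eligible ages 2 to 17 (Protocol 8.1); caregiver questionnaire for ages 2 to 5 (Protocol 9.6.1, SAP 13.1); groups > 2 to < 6 and ≥ 6 (SAP 13.1, 13.2).

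**Step 1: whole years.**

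| Age | Caregiver asked? | Group as written | Group with ≥ 2 |
|---|---|---|---|
| 2 | yes | none | lower |
| 3, 4, 5 | yes | lower | lower |
| 6 to 17 | no (self-rated) | upper | upper |

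Age 2 is the only unassigned age. It is 1 of the 4 whole-year ages that receive the caregiver questionnaire.

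**Step 2: decimal age.** Take age as days/365 for every day from 730 (2.000 years) to 6,569 (the day before 18 × 365 = 6,570). That is 6,569 − 730 + 1 = 5,840 values. Only one, exactly 2.000, is unassigned as written.

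**Step 3: which reading fits the text.** In SAP 13.1 the caregiver population is ages 2 to 5 and the self-rating population is 6 and over. Those two ranges meet without a gap only in whole years, since a decimal age of 5.5 lies outside a literal range of 2 to 5. This favours whole years for this section but does not settle how the age variable is stored.

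**Step 4: other groupings in the SAP.** The youngest category in the demographics (SAP 7.3), the adverse event subgroups (SAP 11.2) and the blood pressure table (SAP 11.4, Table 8) starts at 2. The efficacy subgroup (SAP 9.7) has no lower limit. Only 13.1 and 13.2 print a strict bound at 2. SAP 14, which says it lists every departure from the protocol's analysis, does not mention leaving out 2-year-olds. The exclusion therefore looks unintended.

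**Step 5: after correction.** With ≥ 2 to < 6, every age from 2 to 17 falls in exactly one group, in whole years or as a decimal.

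**The case against.** There are four arguments on the other side.

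**Typography.** The sign may be a ≥ that lost its bar. Protocol 7.2 prints >6 years and >20 kg for Day 1 serial sampling where the synopsis prints ≥, so such slips occur. This cannot be ruled out, but > 2 appears in both SAP sections and the ≥ before 6 is intact beside it each time, so it is unlikely.

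**Intent.** SAP 6.1 calls for all available data to appear in the relevant displays, the Full Analysis Set is all randomized subjects (SAP 6.2), and SAP 15 requires independent review of tables for completeness. This shows that 2-year-olds were meant to be included. It does not tell a programmer which group to put them in.

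**Decimal age.** An upper bound written as < 6 suits continuous age, and the bone age to chronological age ratio in SAP 9.5.4 needs finer age than whole years. If decimal age is also used here, the problem almost disappears. This stands, and it makes the point conditional.

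**Consequence.** The table is descriptive, both arms are cut in the same way, and the endpoint lies outside the fixed testing sequence in SAP 9.1. This also stands.

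A reader might go further and infer that the youngest children are the hardest to dose, so that omitting them flatters acceptability. The documents say nothing about ratings by year of age, so the direction is unknown. A reader might also turn 1 of 4 ages into a quarter of the children, or take 81/16 ≈ 5 children as lost. Both need even enrolment across ages, which the documents do not state. Eligibility also depends on weight, glucocorticoid dose and hormone levels.

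**Conclusion.** The age groups in SAP 13.1 and 13.2 do not match the population given the caregiver questionnaire. If age is held in whole years, every 2-year-old is left out of the Week 4 secondary-endpoint table. With age fixed at consent, the same children are left out at Weeks 28 and 52. If age is held as a decimal, the loss is confined to a child aged exactly 2.000 years. The SAP does not specify which applies, so the defect is conditional. The number affected ranges from zero upwards and cannot be fixed from the documents.

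This is a minor point. No hypothesis test is planned for the ratings, and no primary or key secondary result depends on them. It is still worth correcting, because a programmer who applied the written rule to integer age would drop eligible, assessed children from a secondary-endpoint table.

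**What to change.** In SAP 13.1 and 13.2, write the lower group as ≥ 2 to < 6 years and add that age is taken at initial informed consent, in line with Protocol 9.1. The cost is one changed sign and a short phrase in each of two places. No new data, extra analysis or change to any test is needed.

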## **13.2.** Ease of Administration and Palatability of Study Drug – OL Period

The three questions related to ease of administration, taste, and smell (as described in Section 13.1) will be summarized with descriptive statistics on the OL Period Safety Analysis Set by treatment group, visit (Week 28 [OL baseline] and Week 52), formulation type (oral solution vs. capsule), and age group (> 2 to < 6 years;  $\geq$  6 years).
### 14. DEVIATIONS FROM PROTOCOL PLANNED ANALYSIS

This section will document any deviations from the protocol planned analysis along with any assessments that were performed on study (and reviewed by the study site) but will not be summarized.

The following assessments were performed on study but will not be summarized:

- Physical examination results (excluding height, weight, and Tanner staging)
- CYP21A2 genotyping
- Pregnancy test
- Urine drug screen
- Urinalysis
- Glucocorticoid daily dose from eDiary

The following list includes all deviations from the protocol planned analysis:

- The Safety Analysis Set definition in the protocol specified that the subject must have postbaseline safety data during the double-blind placebo-controlled period. This part of the definition was removed from the SAP due to the potential issue of having a subject dosed with study drug and then becoming lost to follow-up.
- The Safety Analysis Set was split up into the DB Period Safety Analysis Set and the OL Period Safety Analysis Set.

